#### Omaveloxolone drug overdose

Omaveloxolone drug overdose data will be collected for all patients with the following variables:

- Date(s) of the drug overdose
- Daily dose(s) during the overdose

Final protocol version date: 16 December 2024

- Reason for overdose
- Outcome/consequence
  - AE/SAE
    - Overdose-related medical outcomes, in which overdose is defined as any dose higher than the daily recommended dose of 150 mg of omaveloxolone

Protocol reference: 296FA401 (408-C-2301) Final protocol version number: 6.0 Final protocol version date: 16 December 2024

## 9.3.4 Exposure

For the omaveloxolone-naive cohort, treatment characteristics of omaveloxolone will be collected starting at omaveloxolone initiation until the earlier of their end of participation in the study or omaveloxolone discontinuation. For the non-naive cohort, treatment characteristics at baseline will be collected retrospectively at enrollment and then prospectively from enrollment until the earlier of their end of participation in the study or omaveloxolone discontinuation.

The omaveloxolone treatment characteristics will include the following variables:

- Start dates and, as applicable, end dates
- Treatment duration (derived variable)
- Daily dose in mg
- Frequency of administration

Final protocol version number: 6.0

Final protocol version date: 16 December 2024

- Any omaveloxolone treatment change (excluding retrospective changes prior to enrollment in patients in the non-naive cohort) in terms of daily dose or frequency of administration, including omaveloxolone treatment discontinuation
  - Date of change(s)
  - Type of change (dose, frequency)
  - Reason(s) for change
    - Physician decision
    - Patient/parent decision
    - Any SAE or any DILI or CHF AE
    - New-onset comorbidities

#### 9.3.5 Other assessments

#### 9.3.5.1 Collected at the earlier of baseline visit or omaveloxolone treatment initiation

#### Demographics

- Age
- Sex
- Reproductive status (females only)

#### Medical history and comorbidities

- Clinically significant disease and comorbidities of interest, including but not limited to:
  - Cardiomyopathy
  - Other Cardiac conditions
  - Ambulation status
  - Diabetes
  - Scoliosis
- Hepatic impairment (if available prior to omaveloxolone initiation)
  - o Child-Pugh class A
  - Child-Pugh class B
  - Child-Pugh class C
- History of depression (Beck Depression Inventory-2 [BDI-2]) (if available prior to omaveloxolone initiation)

The BDI-2 is a 21-item self-report instrument for measuring the severity of depression in adults and adolescents aged 13 years and older [Beck 1996]. This instrument was developed for the assessment of symptoms corresponding to criteria for diagnosing depressive disorders listed in the American Psychiatric Association's Diagnostic and Statistical Manual of Mental Disorders - Fourth Edition (DSM-IV).

Final protocol version number: 6.0

• History of substance use

#### Anthropometric measurements

- Weight (kg)
- Height (cm)
- BMI (kg/m²), derived from weight and height

#### Clinical characteristics of FA

- Genetic diagnosis
- Family history
- Age at symptom onset
- Age at diagnosis
- Stage of disease
- mFARS and Scale for Assessment and Rating of Ataxia

#### Treatment history

Previous enrollment in a clinical trial for the treatment of FA

## Reproductive status (females only)

- Pregnancies
  - Number of prior pregnancies and fetuses
  - Outcome of each pregnancy
- Lactations
  - Number of prior lactation events
  - Start and end dates

# Recent and concomitant medications (given within 30 days prior to the earlier of baseline visit or omaveloxolone treatment initiation date)

- Prescription drugs
  - Drug name(s)
  - Start and end dates
  - Daily dose
  - Route of administration
  - Indication
  - Reason for treatment discontinuation/withdrawal
- Over-the-counter (OTC) drugs
  - Drug name(s)
  - Start and end dates

Final protocol version date: 16 December 2024

- Daily dose
- Route of administration
- Indication
- Reason for treatment discontinuation/withdrawal
- Herbal or homeopathic remedies
  - Drug name(s)
  - Start and end dates
  - Daily dose
  - Route of administration
  - Reason for treatment discontinuation/withdrawal
- Nutritional supplements
  - Drug name(s)
  - Start and end dates
  - Daily dose
  - Route of administration
  - Reason for treatment discontinuation/withdrawal

## 9.3.5.2 Collected during routine follow-up visits (up to 60 months)

#### Anthropometric measurements

- Weight (kg)
- Height (cm)
- BMI (kg/m²), derived from weight and height

#### Reproductive status (females only)

- Pregnancies
  - Number of pregnancies and fetuses
  - Start and end dates
  - Outcome of each pregnancy
  - Adverse effects on the developing fetus and neonate
- Lactations
  - Number of lactation events
  - Start and end dates
  - Adverse effects on the infant
  - Infant outcomes for at least the first year of life

Final protocol version number: 6.0

Final protocol version date: 16 December 2024

#### Patient status

Death, lost to follow-up, withdrew consent

If applicable: date of death, primary cause of death, date of loss to follow-up, date of consent withdrawal, or reason for consent withdrawal.

#### Concomitant medications (since previous visit)

- Prescription drugs
  - Drug name(s)
  - Start and end dates
  - Daily dose
  - Route of administration
  - Indication
  - Reason for treatment discontinuation/withdrawal
- OTC drugs
  - Drug name(s)
  - Start and end dates
  - Daily dose
  - Route of administration
  - Indication
  - Reason for treatment discontinuation/withdrawal
- Herbal or homeopathic remedies
  - Drug name(s)
  - Start and end dates
  - Daily dose
  - Route of administration
  - Reason for treatment discontinuation/withdrawal
- Nutritional supplements
  - Drug name(s)
  - Start and end dates
  - Daily dose
  - Route of administration
  - Reason for treatment discontinuation/withdrawal

Final protocol version number: 6.0

Final protocol version date: 16 December 2024

# 9.3.5.3 Collected at 60-day safety follow-up (for patients who discontinue study or omaveloxolone treatment)

All SAEs (as defined in Section 9.3.1.1)

- SAE term and its description
- Start and end dates of the SAE
- Outcome of the SAE
- Action(s) taken with omaveloxolone treatment by the treating physician
- Causal relationship to omaveloxolone treatment (per investigator)
- Severity of the SAE
- Hospitalization dates, if applicable

DILI and CHF AEs (as defined in Section 9.3.1.1)

- Start and end dates of the AE
- Outcome of the AE
- Action(s) taken with omaveloxolone treatment by the treating physician
- Causal relationship to omaveloxolone treatment (per investigator)
- Severity of the AE
- Seriousness of the AE
- Date of treatment initiation for the AE

## 9.4 Data sources

Medical information will be recorded in patients' medical records during every routine clinic visit and each time a laboratory test is performed (according to omaveloxolone labeling: monthly during the first 3 months of treatment, and periodically thereafter as clinically indicated; or per the UNIFAI study schedule of assessments). Additional timepoints can be defined if sufficient data are available. Patients' medical record information, research records, and any relevant diagnostic reports are the source documents for study data collection.

As all sites and patients are participating in the UNIFAI study, overlapping data will be extracted from the UNIFAI study where possible to avoid any additional burden to the investigators. When not collected by the UNIFAI study, clinical information recorded in patients' medical records and/or diagnostic reports will be abstracted and entered into the eCRF in the electronic data capture (EDC).

Each patient will have a unique number within the study (Patient Identification). Each site will maintain a Patient Identification list linking the patient to the Patient Identification within the study. Only the investigator and/or authorized personnel will be able to identify the patient based on the Patient Identification list, which will be held only at the site.

The MAH will be the "controller" of the personal data collected for the study. The MAH will take appropriate steps to ensure that personal data are protected.

All SAEs, regardless of causality, as well as pregnancy or lactation-related infant SAE data, will be reported to the MAH's safety vendor within 24 hours of the investigator's knowledge of onset or notification of the

Final protocol version date: 16 December 2024

event. More details on the SAE reporting can be found in Section 11. DILI and CHF AEs and lactation non-SAEs should be reported to the MAH's safety vendor within 7 days (Section 11.2.3.1).

Remote monitoring visits will be conducted by the assigned clinical research associate, as described in the monitoring plan. The monitoring plan will be developed and available before monitoring begins. The eCRFs and patients' corresponding original medical records (source documents) will be fully available for review by the MAH's representatives, as needed, per the monitoring plan. All records at the site are subject to inspection by the local health authority and review by an independent ethics committee (IEC)/institutional review board (IRB).

## 9.5 Study size

The design of the study is descriptive; therefore, no formal sample size or power calculation is necessary. The sample size is based on both practical and statistical considerations. The safety context of the study requires that the sample size be sufficient to detect a signal, if any.

The study will aim to enroll approximately 300 patients. Tables are shown which assess the precision of different sample sizes based on the occurrence of any SAE and the occurrence of all DILI and CHF AEs.

Table 9-4 presents scenarios in which a certain proportion of patients will experience SAEs after 1, 3, and 5 years of exposure duration. This is based on the results of Study 1402 Part 2, in which 5 patients reported SAEs in 51 omaveloxolone-treated patients studied for 1 year and the Poisson SAE rate estimate per patient year was 0.098 [Lynch 2021a]. In Table 9-4, confidence interval widths and precision were calculated based on Poisson distribution. With sample sizes between 100 and 300 of 1, 3, and 5 years of exposure duration, the precision is reasonably tight.

Table 9-4. Sample size precision table for any SAE

	N	Years	Patient- Years	Expected Number of Events	Lower 95	Upper 95	Cl Width	Precision (Cl Width/2)
Primary (any SAE)	100	1	100	9.804	0.047	0.181	0.135	0.067
	100	3	300	29.412	0.066	0.140	0.075	0.037
	100	5	500	49.020	0.073	0.130	0.057	0.029
	200	1	200	19.608	0.060	0.152	0.093	0.046
	200	3	600	58.824	0.075	0.127	0.052	0.026
	200	5	1000	98.039	0.080	0.119	0.040	0.020
	300	1	300	29.412	0.066	0.140	0.075	0.037
	300	3	900	88.235	0.079	0.121	0.042	0.021
	300	5	1500	147.059	0.083	0.115	0.032	0.016

Abbreviations: CI=confidence interval; SAE=serious adverse event

In Table 9-5, confidence interval (CI) widths and precision were calculated using the exact confidence interval of Poisson distribution. With a sample size of 300, the precision is tight for all outcomes: smaller than 4% for the primary outcome and smaller than 3% for the secondary outcome (and with a sample size of 100, smaller than 7% and 5% respectively). Table 9-5 is designed for the objective of documenting the occurrence of all DILI and CHF AEs. There were no safety events of DILI or CHF reported in Study 1402,

Final protocol version date: 16 December 2024

but omaveloxolone has been associated with a higher incidence of ALT and AST increase, and with increases in BNP. For that reason, three different hypothetical rates of DILI or CHF AEs of 1%, 2%, and 5% are presented in Table 9-5.

Table 9-5. Sample size precision table for DILI or CHF AEs

	N	Year	Patient- Years	Rate	Expected Number of Events	Lower Upper 95 95	CI W	/idth	Precision (CI Width/2)
	100	1	100	0.01	1	0.000	0.056	0.055	0.028
	100	3	300	0.01	3	0.002	0.029	0.027	0.014
	100	5	500	0.01	5	0.003	0.023	0.020	0.010
	200	1	200	0.01	2	0.001	0.036	0.035	0.017
	200	3	600	0.01	6	0.004	0.022	0.018	0.009
	200	5	1000	0.01	10	0.005	0.018	0.014	0.007
	300	1	300	0.01	3	0.002	0.029	0.027	0.014
	300	3	900	0.01	9	0.005	0.019	0.014	0.007
	300	5	1500	0.01	15	0.006	0.016	0.011	0.005
	100	1	100	0.02	2	0.002	0.072	0.070	0.035
	100	3	300	0.02	6	0.007	0.044	0.036	0.018
	100	5	500	0.02	10	0.010	0.037	0.027	0.014
DILI or	200	1	200	0.02	4	0.005	0.051	0.046	0.023
CHF	200	3	600	0.02	12	0.010	0.035	0.025	0.012
events	200	5	1000	0.02	20	0.012	0.031	0.019	0.009
	300	1	300	0.02	6	0.007	0.044	0.036	0.018
	300	3	900	0.02	18	0.012	0.032	0.020	0.010
	300	5	1500	0.02	30	0.013	0.029	0.015	0.008
	100	1	100	0.05	5	0.016	0.117	0.100	0.050
	100	3	300	0.05	15	0.028	0.082	0.054	0.027
	100	5	500	0.05	25	0.032	0.074	0.041	0.021
	200	1	200	0.05	10	0.024	0.092	0.068	0.034
	200	3	600	0.05	30	0.034	0.071	0.038	0.019
	200	5	1000	0.05	50	0.037	0.066	0.029	0.014
	300	1	300	0.05	15	0.028	0.082	0.054	0.027
	300	3	900	0.05	45	0.036	0.067	0.030	0.015
	300	5	1500	0.05	75	0.039	0.063	0.023	0.012

Abbreviations: AE=adverse event; CHF=congestive heart failure; Cl=confidence interval; DILl=drug-induced liver injury FA is a rare disease; therefore, the decision was made to utilize the existing UNIFAI study and its infrastructure. This strategy provides an efficient way of finding eligible patients. To capture the outcomes of interest, a total follow-up period of five years will be applied for each patient. Because some patients may not complete all five years of follow-up, some assumptions were made regarding attrition. Table 9-6 presents the expected attrition over the course of the study follow-up.

Final protocol version date: 16 December 2024

Table 9-6. Estimated attrition in patients during the follow-up

Exposure Duration (years)	Anticipated # of Patients Completing Follow-up	PYs
1	260	260
3	230	690
5	180	900

Abbreviation: PY=patient-year

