### 9.1.2 Study duration and follow-up

This study begins after product availability in a country that has approval for omaveloxolone, and when the first participating site begins enrollment, following approval of the protocol by the relevant ethics committee (EC) or institutional review board (IRB). The study start date is December 2024. Each patient's participation will last no longer than 60 months after omaveloxolone initiation, although treatment is expected to continue past this timepoint.

Participation of each patient will begin at the date of informed consent/assent. The index date will be the date at which prospective data collection begins. For the omaveloxolone-naive cohort, this will be the date of initiation of omaveloxolone treatment. For the non-naive cohort, this will be the date of enrollment. After signing informed consent/assent, the patient will be followed for 60 months following date of initiation of omaveloxolone treatment or for 60 days after discontinuation of omaveloxolone treatment or discontinuation from the study. Discontinuation is defined as an interruption in omaveloxolone treatment in which the patient does not reinitiate omaveloxolone treatment within 60 days of the date of the last administration. The date of treatment discontinuation will be defined as the date of the last administration of omaveloxolone. Patients will have completed the study when they complete 60 months of treatment, discontinue treatment and complete the 60-day safety follow-up, withdraw consent, or death. More details on the study time periods are provided in Section 9.2. A study design schematic is presented in Figure 1.

Final protocol version date: 16 December 2024
Figure 1. Study design schematic

Each patient will be asked to provide informed consent/assent for participation in this study and for marketing authorization holder (MAH) access to relevant medical history data. Once informed consent/assent is signed, the patient will receive their study identification (ID) and move to baseline data collection, following which they will be considered enrolled in the study. The initiation date of omaveloxolone treatment will set the study visit cadence, with each visit scheduled based on time passed from this date.

- For the omaveloxolone-naive cohort, baseline data collection will begin following informed
  consent/assent. If omaveloxolone treatment is not initiated at the time of enrollment and

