## 9.7 Data analysis

Details of the planned analyses are summarized below and will be described in a separate statistical analysis plan (SAP).

As previously described, post-baseline study data (including the reporting of any SAEs and potential DILI/CHF events) will only be collected prospectively (i.e. from enrollment into the study). Any retrospective data, changes in treatment regimen, or events that may have occurred between

Final protocol version date: 16 December 2024

omaveloxolone initiation and enrollment in patients in the non-naive cohort will not be collected and will therefore not form part of any analysis.

Data analyses will be presented separately for patients in the omaveloxolone-naive cohort and the non-naive cohort.

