## 9.7.3 Descriptive statistics

Descriptive statistics will be used to summarize the study data in tables, listings, and figures as appropriate at baseline and post-index timepoints. These will cover descriptive analyses of patient demographics, clinical history, disease characteristics, clinical management, . The BDI-2 will be scored as per the developer's guidelines. Continuous variables will be described with summary statistics such as n, mean, standard deviation, median, first quartile, third quartile, and minimum and maximum values. For each categorical variable, the frequency and percentage in each category will be reported. Percentages will be calculated using the specified denominator in the table. The frequency and percentage of patients with missing data for each data point will be presented. Two-sided CIs of 95% will be calculated when relevant. Exact 95% CIs will be calculated assuming a Poisson distribution. Percentages will be reported with one decimal place.

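### The five-year precision in Tables 9-4 and 9-5 rests on 1,500 patient-years that the protocol's own attrition, separate cohorts and late entry will not supply

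*Protocol*

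**What the plan says.** Protocol Section 9.5 sets the target: "The study will aim to enroll approximately 300 patients". For SAEs it takes its rate from the earlier pivotal trial part, where "5 patients reported SAEs in 51 omaveloxolone-treated patients studied for 1 year and the Poisson SAE rate estimate per patient year was 0.098". Table 9-4 (any SAE) and Table 9-5 (DILI or CHF at 1%, 2% and 5%) give 95% interval half-widths for N = 100, 200 and 300 over 1, 3 and 5 years. For N=300 the person-time is 300, 900 and 1,500 PY. The text concludes: "With a sample size of 300, the precision is tight for all outcomes: smaller than 4% for the primary outcome", and below 3% for DILI/CHF, which it calls the secondary outcome. It adds ceilings of 7% and 5% for N=100.

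The same section states that "a total follow-up period of five years will be applied for each patient", then concedes that some will not finish. Table 9-6 expects 260, 230 and 180 patients to complete 1, 3 and 5 years, and lists 260, 690 and 900 PY.

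Three other places bear on this:

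- Section 9.7: "Data analyses will be presented separately for patients in the omaveloxolone-naive cohort and the non-naive cohort".
- Section 9.1.2: "participation will last no longer than 60 months after omaveloxolone initiation". Non-naive patients may enroll up to 12 months after starting treatment (Section 9.2.2.2), and events before enrollment are not collected.
- Sections 8.2.1 and 9.3.1.1 make DILI/CHF a primary objective and a primary outcome.

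**The concern.** The precision tables describe one group of 300 patients, all followed for the full period. The protocol plans something else: two cohorts reported apart, 40% of patients not completing five years (120 of 300), and one cohort whose observed time starts after treatment initiation and stops 60 months after it. Table 9-6 is never carried back into the precision tables, so one section gives the five-year person-time as 1,500 PY in one table and 900 PY in another.

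Neither is the denominator that the rates will use. The abstract defines incidence rates over patient-years at risk during follow-up, and patients who leave are followed until they leave. So 1,500 is too high and 900 is too low.

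Regulators may take the five-year N=300 row as what the registry will deliver. For a rate reported by cohort, the interval will be clearly wider, and no cohort sizes are given that would let a reader pick the right row.

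**Working it through.** **Inputs.** SAE rate 5/51 = 0.09804 per PY; DILI/CHF rates 0.01 and 0.05; N = 300; completers 260, 230 and 180 (all from Section 9.5). Interval method from Section 9.7.3: "Exact 95% CIs will be calculated assuming a Poisson distribution".

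**Formula.** With x = rate × PY, lower = χ²(0.025; 2x)/(2 PY), upper = χ²(0.975; 2x+2)/(2 PY), half-width = (upper − lower)/2.

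**Step 1: reproduce the plan.** Setting PY = N × years returns every row of Tables 9-4 and 9-5 to three decimals. For SAEs at N=300: 0.037 (300 PY), 0.021 (900 PY), 0.016 (1,500 PY). The tables are arithmetically right for their inputs, which contain no attrition and no cohort split.

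**Step 2: what Table 9-6 computes.** 260 × 1 = 260; 230 × 3 = 690; 180 × 5 = 900. This is completers times years, so a patient who leaves at year four adds nothing to the five-year total.

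**Step 3: person-time implied by that retention.** Assuming linear loss between the stated points:

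- Year 1: (300 + 260)/2 × 1 = 280
- Year 3: 280 + (260 + 230)/2 × 2 = 770
- Year 5: 770 + (230 + 180)/2 × 2 = 1,180

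Non-naive time before enrollment must still come off. If half the patients are non-naive with a mean lag of 0.5 years (both assumed), about 150 × 0.5 = 75 PY is lost, leaving about 1,105.

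**Step 4: five-year half-widths.** Cohort rows use an assumed split and, unless stated, no entry lag.

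| Group | PY | SAE | DILI/CHF 1% | DILI/CHF 5% |
|---|---|---|---|---|
| Printed, N=300 | 1,500 | 0.0162 | 0.0054 | 0.0117 |
| Pooled, implied | 1,180 | 0.0183 | 0.0062 | 0.0132 |
| Pooled, Table 9-6 | 900 | 0.0210 | 0.0072 | 0.0152 |
| Cohort of 150 | 590 | 0.0262 | 0.0091 | 0.0190 |
| Cohort of 100 | 393 | 0.0323 | 0.0116 | 0.0236 |
| Cohort of 100, 0.5-year lag | 343 | 0.0347 | 0.0125 | 0.0253 |

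For SAEs, 0.0183/0.0162 = 1.13 (13% wider) pooled, and 0.0262/0.0162 = 1.62 (62% wider) for a cohort of 150.

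**Step 5: the 4% and 3% ceilings.** They match the one-year N=300 rows (0.037; 0.027 at a 5% rate). By the formula above they need about 263 and 251 PY.

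| One year | PY | SAE | DILI/CHF 5% |
|---|---|---|---|
| Pooled, implied | 280 | 0.0387 | 0.0283 |
| Pooled, Table 9-6 | 260 | 0.0402 | 0.0294 |
| Cohort of 150, no attrition | 150 | 0.0540 | 0.0399 |
| Cohort of 200, no attrition | 200 | 0.0463 | 0.0340 |

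Pooled, both ceilings hold on the implied 280 PY. By cohort, both fail at one year, even for the larger cohort of a 200/100 split. At five years both hold for each cohort in Step 4.

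**The case against.** A reader might infer that the 4% and 3% claims themselves are false. The documents do not support that. These are ceilings set by the least favourable N=300 row. At study end they survive attrition, and they survive cohort separation for splits between 100/200 and 200/100, with half a year of entry lag as well. The only pooled breach, 0.0402 at one year, relies on the 260 PY that discards leavers' time; on 280 PY it disappears.

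A reader might also infer that nothing in Section 9.5 speaks to smaller groups. It does: rows for N=100 and N=200 are printed, the N=100 ceilings are quoted, and a 150-patient cohort at one year (5.4%, 4.0%) lies inside them. Attrition is disclosed in the same section, Section 9.9.1 admits limited precision, and Section 9.7.7 plans SAE counts for the whole study population, so a pooled figure has some use. The study is descriptive, and its size rests on practical as well as statistical grounds, so it would be too much to say that the choice of 300 depends on these figures.

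All of this stands, and it limits the weight of the point. It does not reconcile 1,500 PY with Table 9-6, make completers times years a person-time total, or tell a reader which row applies to either cohort.

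**Conclusion.** The point holds for the tabulated person-time and the five-year precision, and should be fixed. The N=300 rows ignore attrition, cohort separation and late entry; Table 9-6 errs in the opposite direction. The printed five-year SAE half-width of 0.016 becomes about 0.018 pooled and about 0.026 per cohort. For DILI/CHF at 1%, 0.005 becomes about 0.006 and 0.009. The 4% and 3% ceilings are sound as pooled figures but not for cohort-specific one-year rates.

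The magnitudes rest on three assumptions absent from the protocol: linear loss between the stated retention points, a 150/150 split, and, where used, a mean entry lag of 0.5 years. A cohort smaller than 100 would do worse: one of 60, with about 236 PY, has a five-year SAE half-width of 0.042. The person-time conflict and the outcome label do not depend on any split.

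**What to change.** Keep the target of about 300 patients and amend Section 9.5:

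1. Recompute Table 9-6 as cumulative person-time from the retention curve (about 280, 770 and 1,180 PY under linear loss), subtract pre-enrollment time for non-naive patients, and state the assumptions.
2. Restate the precision in Tables 9-4 and 9-5 on that person-time, for each cohort, over a stated range of splits such as 100/200, 150/150 and 200/100.
3. Say that the 4% and 3% ceilings are pooled figures, and give the one-year cohort figures beside them.
4. Qualify the statement that every patient has five years of follow-up, since non-naive patients cannot.
5. Relabel DILI/CHF as a primary outcome.

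The cost is one rewritten section and a less favourable stated precision. No patients, visits or analyses are added.
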